## **Biopsy**

Chronic nephrotoxicity from calcineurin-inhibitors (CI) has been implicated as a principal cause of post-transplant renal dysfunction and it is characterized by an irreversible and progressive tubular atrophy, interstitial fibrosis, and focal hyalinosis of small renal arteries and arterioles. Furthermore, chronic nephrotoxicity from CI has been documented in all non-renal transplants and the chronic renal failure secondary to the use of CI has been associated with an increase in mortality by a factor of more than four.

The present proposal is to identify those subjects already participating in this study who are willing to undergo a kidney biopsy with the aim of evaluating renal allograft pathology and renal allograft tissue gene expression profiles of the two groups of patients maintained on Tacrolimus/ MMF or switched to SRL/MMF. Performing kidney biopsies on the subjects who consent for the procedure will allow us to address the effect of immunosuppressive modifications on renal allograft pathology at 24 months post randomization. We also plan to obtain renal allograft biopsies at 12 months post-transplant (standard of care) in order to establish a baseline parameter for to compare the 24 month sample. An additional biopsy at 48 months will allow us to examine long term results of graft function. We also plan to obtain renal allograft biopsies to be stored in RNA later to further extend our knowledge on the effect of CI free immunosuppression on gene expression profiles.

Obtaining renal allograft tissue samples at 24 and 48 months post randomization can have potential important ramifications to help explain the mechanisms of fibrosis and tubular atrophy typically associated with CI and the role of CI elimination with the substitution of SRL. All data will then be analyzed comparing gene expression profiles of peripheral blood (Paxgene tubes are routinely collected at the different time points as part of the original study). Based on power analysis, we will perform 24 and 48 months post randomization biopsies in 70% of the total subjects enrolled in the study (approximately 46 subjects from the tacrolimus/MMF group and approximately 93 subjects from the sirolimus/MMF group).

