### **Randomization**

For this research study, between 6 and 24 months post-transplant we plan to prospectively randomize 2:1 renal transplant patients to either:

- Continue with tacrolimus and MMF or
- Substitute tacrolimus with sirolimus and continue MMF

A total of 400 pts. are expected to be screened for the randomization and we expect to be able to randomize 275 renal transplant patients into this protocol.

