## **Study drugs**

### **Sirolimus (Rapamune®)**

Sirolimus will initially be given at a dose of 2-4 mg orally (PO) daily. The dose will be modified to achieve 24 hours trough concentrations of 6-10 ng/ml by HPLC assay. This medication will be given in an open label fashion. The first dose of sirolimus will be given at the time of randomization to those patients assigned to have tacrolimus switched to sirolimus.

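### Biopsy volunteers come from subjects who, by inference, already know their open-label arm, so randomisation no longer guarantees an unbiased 24- and 48-month pathology comparison

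*Combined protocol and SAP*

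**What the plan says.** The Biopsy section describes an addition to a running trial. It proposes to "identify those subjects already participating in this study who are willing to undergo a kidney biopsy" and defines the groups by the treatment they are on: "two groups of patients maintained on Tacrolimus/ MMF or switched to SRL/MMF". It reads a treatment effect from the volunteers: "Performing kidney biopsies on the subjects who consent for the procedure will allow us to address the effect of immunosuppressive modifications", judged on pathology at 24 months, with a further biopsy at 48 months. The target is 70% of those enrolled, given as "approximately 46 subjects from the tacrolimus/MMF group and approximately 93 subjects from the sirolimus/MMF group".

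On blinding, the sirolimus entry under Study drugs says "This medication will be given in an open label fashion", and the tacrolimus entry says the same. It adds: "The first dose of sirolimus will be given at the time of randomization to those patients assigned to have tacrolimus switched to sirolimus".

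The Statistical Analysis section names two-sample t tests, chi-square tests, and a multivariable logistic model for acute rejection and renal function. It does not mention the biopsy subset. The protocol describes no biopsy consent before randomisation, no random or consecutive choice of biopsy subjects, no comparison of those biopsied with those not, and no sensitivity analysis.

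**The concern.** The biopsy comparison is meant to show whether replacing the calcineurin inhibitor changes fibrosis and tubular atrophy. Randomisation makes the two full arms comparable. It makes two volunteer subsets comparable only if volunteering, and still being in the study at the biopsy visit, relate to graft condition in the same way in both arms.

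Nothing in the design ensures this. The drug is known, and the Post randomization section provides monthly laboratory tests in both arms, so subjects and investigators can see how the graft is doing. Someone with falling function on a new drug and someone with falling function on the familiar one may answer a biopsy request differently. Differential consent of that kind could create a pathology difference or hide one. A larger sample would not remove it, and equal uptake in the two arms would not show its absence.

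**Working it through.** **1. The participation figure.** Inputs: 70% and 46 + 93 = 139 (Biopsy section); "we plan to prospectively randomize 2:1 renal transplant patients to either" and "we expect to be able to randomize 275 renal transplant patients into this protocol" (Randomization section).

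- 70% of 275 is 192.5, or about 64 + 128 when split 1:2. This does not reproduce 46 + 93.
- 139 / 0.70 = 198.6. With 200 enrolled, 70% is 140, or 46.7 + 93.3, which does agree.
- 139 / 275 = 50.5%.

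Participation is therefore 70% as stated, or about 50% if 139 are biopsied out of 275. The documents do not settle which applies, so both are carried forward. The power analysis that the section mentions cannot be reproduced, because its alpha, power, effect size and SD are not given.

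**2. Scale of the comparison.** Assume SD = 1, two-sided alpha 0.05 and 80% power. The standard error is √(1/46 + 1/93) = 0.180. The detectable difference is (1.96 + 0.84) × 0.180 = 0.505 SD, about 0.51 SD.

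**3. Bias if consent depends on graft condition in one arm only (assumption).** Let graft condition X be standard normal with no true treatment effect. In one arm, P(consent | X) = 1 / (1 + exp(−a − X·ln OR)), with a chosen to give the stated uptake f. In the other arm consent is unrelated to X. The bias is E[X·P(consent | X)] / f, found by numerical integration. The false-positive rate is that of a nominal 5% test with standard error 0.180.

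| Odds ratio per SD | Bias at 70% | False positives at 70% | Bias at 50.5% | False positives at 50.5% |
|---|---|---|---|---|
| 1.25 | 0.07 SD | 7% | 0.11 SD | 9% |
| 1.5 | 0.12 SD | 10% | 0.19 SD | 19% |
| 2.0 | 0.19 SD | 18% | 0.31 SD | 40% |

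**4. The zero end.** If consent depends on X equally in both arms, and uptake is the same, the two shifts cancel. The bias is 0 and the false-positive rate stays at 5%.

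**5. Does the earlier biopsy supply a baseline?** The Biopsy section plans a standard-of-care biopsy at 12 months post-transplant for comparison with the 24-month sample. Randomisation takes place 6 to 24 months post-transplant. For a subject randomised at 6 months, that biopsy falls 12 − 6 = 6 months after assignment. For one randomised at 24 months, it falls 24 − 12 = 12 months before. It is not a consistent pre-treatment measurement.

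**6. Losses before the biopsy.** The Stopping Rules section removes subjects from the study after two rejections following conversion, a rule worded only for the sirolimus arm. For withdrawn subjects, the follow-up section promises an attempt at survival data at least and does not mention biopsy. Remaining available for biopsy may therefore also differ by arm.

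**The case against.** The strongest reply has five parts.

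- **Timing is inferred.** No passage dates the biopsy consent. Knowledge of arm follows from the reference to subjects already in the study, the on-treatment description of the groups and the open-label design. Consent forms were not available and might say more. This stands. A reader might infer that consent is usually sought after months of treatment, but the documents do not say so.
- **Bias is possible, not shown.** Nothing in the documents indicates that consent depends on graft condition differently by arm. This also stands. A reader might infer that the protection of randomisation is lost outright; what the text supports is that it is no longer guaranteed.
- **The size is modest.** Even the largest bias in the table, 0.31 SD, is below the 0.51 SD detectable difference, and it needs the lower participation. A reader might take half of each arm as the planned sample, but the protocol states 70%, where the range falls to 0.07 to 0.19 SD. This is fair as to size, although at that 70% the false-positive rate still reaches 18% in the worst case shown.
- **There is a baseline biopsy.** It may reduce selection on existing damage, but its timing relative to randomisation varies from 6 months after to 12 months before, so it does not cure the problem.
- **The component is peripheral.** Biopsy pathology is not among the primary or secondary aims in the Research Objective section, research biopsy has to be voluntary, and consent before assignment is impossible for subjects already randomised. All of this is true. It limits the weight of the point and shapes the remedy, but it does not supply the missing analysis.

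**Conclusion.** The concern holds in a limited form. Biopsy subjects are volunteers who, by inference, know their arm; a treatment effect is to be read from them; and the only group comparisons specified are unadjusted. Randomisation therefore does not guarantee an unbiased comparison of pathology or tissue gene expression at 24 and 48 months.

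The possible bias runs from zero (equal dependence in both arms) to about 0.19 SD at 70% participation or 0.31 SD at about 50%. The upper figures assume one-sided dependence with an odds ratio of 2.0 per SD and no true effect. Against a detectable difference of 0.505 SD, they are 0.19/0.505 = 38% and 0.31/0.505 = 61% of it. Neither the odds ratios nor the alpha and power behind the detectable difference come from the documents.

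The rejection endpoint, which does not rest on the biopsy volunteers, is unaffected. This is a minor point about an add-on component, worth correcting because the correction is cheap.

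**What to change.** - **Subjects still to be randomised:** ask for voluntary biopsy consent at enrolment, before the arm is revealed. This does not prevent later refusal or withdrawal, so report both by arm.
- **Subjects already randomised:** tabulate biopsied against non-biopsied subjects by arm on the variables the Data Collection section already gathers at randomisation: eGFR, proteinuria, rejection history, donor age and donor type.
- **Analysis:** add a baseline-adjusted analysis, or one weighted by the inverse probability of being biopsied, as a sensitivity analysis. State that it corrects only measured baseline selection, and not selection on the course after randomisation or on withdrawals.
- **Reporting:** for subjects whose consent followed assignment, describe the pathology comparison as non-randomised.
- **Participation:** state which number enrolled the 70% refers to, so that 46 + 93 can be reconciled with 275.

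The cost is a small change in consent timing, a modest extra analysis and somewhat wider intervals. No additional biopsies are needed.

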### **Data Collection**

The following data will be collected at the time of randomization:

Recipient demographics- such as age at transplantation, sex and race.

Clinical history- Causes of end-stage renal disease, past medical history

Transplant related information- donor age, cadaveric versus living kidney transplant, histocompatibility and cross match data, viral serology, history of acute rejection and delayed graft function, use of induction therapy and immunosuppressants, use of ACEI and/or ARB, level of renal allograft function- estimated GFR (e-GFR(12) using MDRD formula, proteinuria.

Peripheral blood leukocytes will be obtained from renal transplant recipients for baseline (prior to randomization) lymphocytes functional activity and characterization of lymphocytes subpopulations by flow cytometry analysis.

Peripheral donor leukocytes (from living donor patients) will also be obtained at the time of randomization. These donor leukocytes will be used as stimulator cells to study the functional activity of the recipient's lymphocytes function.

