## **Statistical Analysis**

Once the 2 groups of renal transplant patients are identified, two sample t tests will be used to compare differences in continuous variables between groups; chi square tests will be used to compare differences in discrete variables. Multivariable logistic regression analysis will be also performed to identify the combination of clinical variable that are significantly associated with the development of acute rejection and renal allograft function after conversion from tacrolimus →sirolimus.

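### The baseline biopsy is timed from transplant, not randomisation, so it can fall up to 6 months after the switch to sirolimus or up to 12 months before randomisation, and no rule covers this

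*Combined protocol and SAP*

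**What the plan says.** The combined protocol and SAP times the biopsies on two different clocks.

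- **Baseline biopsy, counted from transplant.** Biopsy section: "We also plan to obtain renal allograft biopsies at 12 months post-transplant (standard of care) in order to establish a baseline parameter". The stated purpose is comparison with the 24-month sample.
- **Follow-up biopsies, counted from randomisation.** The same section aims to "address the effect of immunosuppressive modifications on renal allograft pathology at 24 months post randomization", and adds a further biopsy at 48 months post-randomisation.
- **Entry window.** Randomization section: "between 6 and 24 months post-transplant we plan to prospectively randomize 2:1 renal transplant patients".
- **Start of the switch.** Sirolimus section: "The first dose of sirolimus will be given at the time of randomization".

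For the blood samples, the baseline is tied to randomisation. Data Collection section: "Peripheral blood leukocytes will be obtained from renal transplant recipients for baseline (prior to randomization) lymphocytes functional activity".

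The biopsies are voluntary; the section seeks to "identify those subjects already participating in this study who are willing to undergo a kidney biopsy". The planned numbers are "approximately 46 subjects from the tacrolimus/MMF group and approximately 93 subjects from the sirolimus/MMF group". The Statistical Analysis section does not mention biopsies. For continuous outcomes it says only that "two sample t tests will be used to compare differences in continuous variables between groups".

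**The concern.** A baseline should describe the graft before the assigned treatments diverge. Month 12 post-transplant lies inside the 6-to-24-month entry window, so the baseline biopsy can fall on either side of randomisation.

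For a sirolimus subject randomised early, the tissue called baseline has already been exposed to sirolimus. Taking change from it, or adjusting for it, could absorb part of the effect under study. A tacrolimus subject randomised early has had no change of drug, so this contamination is confined to one arm.

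For a subject randomised late, in either arm, the baseline is old. Further time on tacrolimus passes between the biopsy and randomisation, and the span over which change is measured becomes longer.

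The plan does not limit the biopsy subset to subjects randomised after month 12, does not require the baseline biopsy to precede randomisation, and does not say how a post-switch sample is used. Without a rule, which samples count as baseline could be decided after the data are seen. At stake is the baseline-to-24-month comparison that the Biopsy section sets up.

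**Working it through.** The plan gives no figure to reproduce here; the check is date arithmetic.

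**Inputs from the documents.** Month of randomisation r, from 6 to 24 post-transplant (Randomization). Baseline biopsy at month 12 post-transplant and follow-up biopsy at month r + 24 post-transplant (Biopsy). First sirolimus dose at month r (Sirolimus section).

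**Timing.**
- Baseline relative to randomisation = 12 − r (positive means after randomisation).
- Baseline to 24-month biopsy = (r + 24) − 12 = r + 12.

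| Randomised at month r | Baseline relative to randomisation (months) | Baseline to 24-month biopsy (months) |
|---|---|---|
| 6 | +6 | 18 |
| 9 | +3 | 21 |
| 12 | 0 | 24 |
| 18 | −6 | 30 |
| 24 | −12 | 36 |

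The longest delay after the switch is 6 months, the oldest baseline precedes randomisation by 12 months, and the interval to follow-up varies from 18 to 36 months. The interval varies in both arms.

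**Share randomised before month 12.** The documents do not give it. Assuming entry is uniform over the window, p = (12 − 6)/(24 − 6) = 1/3. An assumed range of 10% to 70% is carried below.

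**Counts, with a caveat.** On the planned 93 sirolimus biopsies, uniform entry gives 93 × 1/3 = 31 affected (9 to 65 over the assumed range). However, 46 + 93 = 139, which is 139/275 = 50.5% of the 275 subjects expected to be randomised, whereas the Biopsy section describes these numbers as 70% of those enrolled. Seventy percent of 275 is 192.5, or about 64 and 128 by arm; on 128, uniform entry gives about 43 affected. The share is a safer guide than the counts.

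**Illustration of size.** Two further assumptions are needed, neither from the documents: the analysis is a between-arm contrast of change from baseline, and the effect builds linearly over 24 months. The fraction of the 24-month effect already present at the biopsy is then (12 − r)/24.
- r = 6: 6/24 = 25%.
- Mean for r uniform on 6 to 12: 3/24 = 12.5%.
- Loss in the arm-level contrast: 0.125 × p = 4.2% at p = 1/3 (1.25% at p = 0.10; 8.75% at p = 0.70).

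An effect that appears faster would give a larger loss, which the documents do not allow to be estimated.

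**Precision if early-randomised subjects are left out of the baseline comparison.** Standard error multiplier = 1/√(1 − p) = 1/√(2/3) = 1.22 (1.05 at p = 0.10; 1.83 at p = 0.70). The multiplier does not depend on the 46 and 93.

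**The case against.** The strongest reply is that the harm needs an analysis that the plan never specifies. The Statistical Analysis section gives between-group tests, which fit a direct comparison of the 24-month samples, and that comparison does not use the baseline. This stands in part. The documents show an ill-defined baseline, not a biased result; but the Biopsy section does say the baseline is there to be compared with the 24-month sample, so it is meant to be used.

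Second, the remedy may cost more than the problem: a 22% larger standard error set against an illustrated loss of about 4%. Bias and precision are not interchangeable, and the 4% rests on assumed entry and an assumed linear effect. The trade is still real, and it is the reason for making the restricted comparison secondary. Reporting the biopsy-to-switch interval with a sensitivity analysis would cost less, but would still leave open which samples count as baseline.

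Three stronger readings might be inferred, and the documents do not support them.

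- **That all the distortion lies in the sirolimus arm.** Exposure to sirolimus at baseline is one-sided, but stale baselines and unequal intervals occur in both arms.
- **That a gene-expression baseline is contaminated.** The sentence on storing tissue for RNA gives no time point, and whether month-12 tissue is stored for this is not stated.
- **That the trial's main result is at risk.** The primary aim is acute cellular rejection, and graft histology is not among the aims listed under Research Objective.

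**Conclusion.** The point holds as a minor defect in a voluntary sub-study. The mismatch of clocks and the absence of a handling rule follow directly from the text: baseline from 6 months after to 12 months before randomisation, and a baseline-to-follow-up interval of 18 to 36 months.

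The consequence arises only if the baseline enters the analysis, as change or as a covariate. Its size is unknown. It is probably small for histology, because the Biopsy section describes scarring that accumulates over time and does not regress; the 4% figure is an illustration, not an estimate. The direct comparisons between arms at 24 and 48 months do not use the baseline and are unaffected by this problem.

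**What to change.** Amend the Biopsy and Statistical Analysis sections as follows.

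1. Make the between-arm comparison of the 24-month (and 48-month) post-randomisation biopsies the main biopsy analysis, adjusted for time from transplant to randomisation.
2. Count a 12-month biopsy as baseline only if its actual date is on or before the day of randomisation. Apply the same rule in both arms, and report later ones as early post-randomisation samples.
3. Treat the comparison with baseline as secondary, restricted to subjects with a valid baseline, adjusted for the same timing covariate, with numbers reported by arm. With the biopsy at month 12, the interval to follow-up among these subjects is r + 12, that is 24 to 36 months, so the covariate captures it directly.
4. Attach to any absolute count built on 46 and 93 the caveat that these do not equal 70% of 275, until the numbers are reconciled.

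This is wording only: no biopsy is added or moved. The price is precision in the secondary comparison, which loses early-randomised subjects in both arms: about one third under uniform entry, with a standard error about 22% larger. The main comparison keeps every subject with a follow-up biopsy.

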## **Donors**

Donor cells are essential in our study to evaluate the effect of different immunosuppressive agents alone or in combination on the process of allo-recognition. Donor cells from living donors have been being collected (there is a specific informed consent form for donors) and will continue to be collected when possible. Approximately 275 donors will be recruited for this study.

While the process of obtaining donor cells from living donors is easy, recipients of a deceased donor kidney have, by definition, no living donor. Consequently, we cannot fully study their immune system. Instead, we would like to utilize already stored deceased donor cells to perform the experiments originally proposed in our ongoing project. We will use only donor cells from deceased donors whose families have consented to research.

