## **Subject Selection and Withdrawal**

The study will be conducted at Northwestern Medical Faculty Foundation/Northwestern Memorial Hospital/ Northwestern University and subjects will be recruited from the patients seen in the Division of Solid Organ Transplantation. A total of 400 recipient subjects will be screened and we expect that 275 recipients will be prospectively studied. The study will be conducted in recipients of living donor kidneys and deceased donor kidneys. Patients who satisfy the following inclusion/exclusion criteria will be eligible for the study.

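### The 275 donors to be recruited equal the 275 recipients although deceased-donor recipients are eligible, and the analysis ignores which of two stimulator-cell sources was used

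*Combined protocol and SAP*

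**What the plan says.** The Randomization section gives the recipient numbers: "A total of 400 pts. are expected to be screened for the randomization and we expect to be able to randomize 275 renal transplant patients". Subject Selection and Withdrawal defines who they are: "The study will be conducted in recipients of living donor kidneys and deceased donor kidneys".

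Donor leukocytes serve as stimulator cells in the recipient functional assay. Data Collection names one source for them: "Peripheral donor leukocytes (from living donor patients) will also be obtained at the time of randomization".

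The Donors section is wider. Its first paragraph describes living donors, who have their own consent form and whose cells "will continue to be collected when possible", and ends: "Approximately 275 donors will be recruited for this study". Its second paragraph notes that "recipients of a deceased donor kidney have, by definition, no living donor", and continues: "Instead, we would like to utilize already stored deceased donor cells to perform the experiments originally proposed in our ongoing project". It adds a limit: "We will use only donor cells from deceased donors whose families have consented to research".

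Statistical Analysis provides two-sample t tests for continuous variables and chi-square tests for discrete ones. Its one multivariable model is for acute rejection and renal allograft function. Donor type appears in neither the randomisation scheme nor the analysis, although Data Collection records whether each kidney came from a living or a deceased donor.

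**The concern.** The donor figure looks as if it was set at one per recipient without allowing for recipients who have no donor to recruit. A reader cannot tell from it how many recipients will have living-donor stimulator cells, how many will rely on stored deceased-donor cells, and how many will have neither.

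The second part matters more for the analysis. Two cell sources feed one assay. If responses differ in level by source, that difference enters the residual variance of an unadjusted comparison and blurs the contrast between tacrolimus and sirolimus. What is at stake is precision in the donor-stimulated part of secondary aim iv (lymphocyte function). Flow cytometry of subpopulations, the other secondary aims and the primary rejection endpoint do not depend on donor cells.

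**Working it through.** **Inputs from the protocol.** Donors to be recruited: about 275 (Donors). Recipients to be randomised: 275 of 400 screened (Randomization). Allocation: 2:1 (Randomization). Donor types: both, split not given (Subject Selection and Withdrawal). Stored deceased-donor samples: number not given (Donors). Sample size for the lymphocyte assay: none stated.

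**Step 1: reproduce the figure.** The documents give no derivation of the 275 donors. The match is one donor per randomised recipient: 275 x 1 = 275.

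**Step 2: what 275 living donors would require.** Living donors available = 275 x L, where L is the share of recipients with a living donor. Allowing 3% for the word approximately, 0.03 x 275 = 8.25, so at least 275 - 8.25 = 266.75 are needed, and L must be at least 266.75 / 275 = 0.97.

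**Step 3: the range under assumed L.** L is an assumption throughout. Counts are rounded to whole donors (halves to the even number). The smaller arm is one third. The last column is the standardised difference detectable if only living-donor pairs were used, with assumed 80% power and two-sided alpha 0.05:

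d = (1.960 + 0.842) x sqrt(1/m + 1/(2m)), with m the size of the smaller arm.

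| L (assumed) | Living donors | Below 275 by | Smaller arm | d (SD) |
|---|---|---|---|---|
| 100% | 275 | 0 | 92 | 0.36 |
| 90% | 248 | 27 | 83 | 0.38 |
| 80% | 220 | 55 | 73 | 0.40 |
| 70% | 192 | 83 | 64 | 0.43 |
| 60% | 165 | 110 | 55 | 0.46 |
| 50% | 138 | 137 | 46 | 0.51 |
| 40% | 110 | 165 | 37 | 0.57 |

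For example, at 40%: m = 110/3 = 36.7, and 2.802 x sqrt(1.5/36.7) = 0.57. At an assumed 40-70%, the living-donor count is 30-60% below 275 (83/275 and 165/275). The d column is a limiting case, because the plan also intends to use stored cells.

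**Step 4: the alternative count.** If 275 covers both sources, living donors plus stored samples = 275 x L + 275 x (1 - L) = 275 at any L, provided a consented stored sample exists for every deceased-donor recipient and a living-donor sample for every other one. The documents confirm neither condition.

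**Step 5: what ignoring source costs.** Suppose responses have variance V within source, and mean responses differ by D between sources. With a share p of recipients in one source, the pooled within-arm variance is V + p(1 - p)D². For p from 0.40 to 0.70, p(1 - p) runs from 0.70 x 0.30 = 0.21 to 0.50 x 0.50 = 0.25. The unadjusted t test therefore carries an extra 0.21-0.25 times D², and an analysis within source removes it. The documents give neither D nor V, so the gain cannot be turned into a percentage.

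**The case against.** A reader might infer that 275 donors is impossible, or that the assay's sample size is overstated. The documents support neither. The 275 is an approximate recruitment figure, and no assay sample size is stated for it to contradict. The Donors section recognises that deceased-donor recipients have no living donor and supplies stored cells for them, so a combined total near 275 is possible (step 4). One could also set the donors against the 400 screened, where 275/400 = 69% would be enough. But Data Collection places donor sampling at randomisation, which makes 275 the likelier denominator.

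A reader might also infer that mixing sources biases the arm comparison. Randomisation balances donor type in expectation, and the t test's error rate already allows for chance imbalance. Aim iv is framed as before versus after conversion, with a pre-randomisation sample. If a recipient's donor source stays the same across visits, changes from baseline remove much of the level difference. That is a fair point, although Statistical Analysis does not specify a change-from-baseline comparison, and a response to conversion that differs by source would not cancel.

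Nor do the documents establish a contrast of fresh against stored cells. Living donors give a single blood sample (Subject Stipends or Payments), while recipient sampling runs to 48 months, so living-donor cells may well be stored too. How they are handled is not described.

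Three things stand. The recruitment sentence follows directly on the living-donor consent form, and already stored cells are not recruited, so the living-donor reading is the natural one. Data Collection and Donors disagree on the sources. And no analysis rule separates them.

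**Conclusion.** The point holds as one of clarity and precision. Read as living donors, about 275 is attainable only if almost every recipient (about 97%) has one. The shortfall cannot be sized from the documents; 110-192 living donors is what an assumed 40-70% share would give, and under the combined reading there may be no shortfall. The plan uses two stimulator sources, names only one of them in Data Collection, and compares arms with an unadjusted t test.

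The consequence is mainly added variance in the donor-stimulated part of secondary aim iv, of a size that depends on an unknown difference between sources. It is not a systematic bias, it does not make the 275 impossible, and it leaves the primary endpoint alone. It is a minor point, worth making because the remedy is nearly free.

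**What to change.** 1. **Donors:** replace 275 with two expected numbers, one for living donors among the 275 recipients and one for deceased-donor recipients with a usable, consented stored sample. State whether the stored cells come from the recipient's own donor, which the text leaves open.
2. **Data Collection:** name both sources of stimulator cells, in line with Donors.
3. **Statistical Analysis:** add a sentence such as: *The donor-stimulated assay will be compared between arms within stimulator source (living donor, stored deceased donor), and the two arm differences will be combined with inverse-variance weights; equivalently, stimulator source will be a term in a linear model with treatment arm.* The donor type already recorded at randomisation supplies the variable.

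The cost is a less favourable donor count on paper and one extra model term. No additional samples, visits or recipients are needed.
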